#### 4.5 Minimization of Bias

The study will enroll all eligible patients identified during the determined enrollment period at each site. The inclusion of all ‘eligible’ patients minimizes any potential for bias in the selection of patients for participation in this registry.

#### 4.6 Data Collection

No data will be collected solely for the purposes of this study. All data elements will be collected from information routinely recorded in the EHR or other relevant data sources (e.g., a standalone PRO platform). No visits or examinations, laboratory tests or procedures are mandated as part of this study. In addition, the app will be implemented locally, meaning that no data will leave the health system IT systems. The app will have the ability to transmit data externally (e.g., to a patient registry), but this feature will not be activated during the pilot study.

The capture of PROs, specifically the PHQ-9, at regular intervals is critical for implementation of the depression outcome measures. Practices participating in this pilot project will capture the PROs at regular intervals (including outside of clinical visits with reminders sent to patients) using a standalone PRO system implemented within the health system. This is done as part of routine clinical care for patients with depression, and data captured in this manner are used to calculate quality measures for submission to the Centers for Medicare and Medicaid Services under the Merit-based Incentive Payment System (MIPS).

##### 4.6.1 Data Elements

The following data will be collected for all patients (if available in the EMR or other existing data sources):

##### Patient Characteristics

- Sex
- Age

- Race/ethnicity
- Family history of depression and other major mental illnesses
- Socioeconomic status
- Pregnancy/Postpartum status

#### Disease

- Comorbidities
- Disease course
  - Type of depressive episode
  - Depressive severity at diagnosis
  - Duration of symptoms
  - Previous relapses/prior history of depression
  - Prior treatments, including number of medications and number of failed antidepressant treatment attempts
  - Lab tests (e.g., thyroid function, metabolic indices, inflammatory markers)
- Suicidality

#### Treatments

- Type
  - Medications (type, dose, duration, adherence)
  - Psychotherapy
  - Devices (type, dose, and duration)
  - Alternative
- Referral(s) for treatment

#### Outcomes

- Death from Suicide
- Improvement in depressive symptoms (assessed via PHQ-9 scores)
  - Response
  - Remission
- Worsening in depressive symptoms
  - Recurrence (PHQ-9 score, hospitalization data)
- Adverse events
- Suicide Ideation and Behavior (assessed via PHQ-9, diagnosis codes)

## 5. Qualitative Assessment

No formal statistical analysis is planned for this pilot study, and no sample size calculations were done. We anticipate that approximately 50 patients enrolled at five practices will be sufficient to address the objectives of this pilot study.

The purpose of this analysis is to assess the feasibility and value of the open-source app. Clinicians and other personnel (e.g., IT staff) at participating practices will be asked to complete a brief web-based survey at the conclusion of the data collection period to provide feedback on the app. The survey will contain approximately 20 questions assessing three domains: usability of the app, burden of using the app, and overall value of the app for informing patient care and improving engagement with patients. Results of the survey will be summarized in a final study report and in a publication. No patient data will be included in the assessment phase.

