### **3. Objectives**

The purpose of this pilot study is to demonstrate feasibility and value of collecting a subset of the harmonized outcomes measures for MDD in the primary care and mental health setting.

Objectives:

[figure not shown]
- Demonstrate that it is technically and operationally feasible to use an open-source app to extract the selected outcome measures, including PHQ-9 information, from existing clinical systems and provide the calculated measure results in the clinician’s workflow.
- Assess burden of capturing the measures from patients (PHQ-9) and clinicians and value of providing the measure results.

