### **4. Study Design**

#### **4.1 Study Description**

The study is a longitudinal, observational pilot study that will assess the utility and value displaying the harmonized outcomes data to clinicians in the clinical workflow using an open-source, SMART on FHIR app. The app will connect with the site EHR, aggregate EHR and PRO data, calculate the outcome measure results, and return the results to the EHR so that they are viewable within the clinician workflow. Baseline data on patient characteristics, treatments, and symptoms will be combined with longitudinal data on outcomes during the study timeframe (see Figure 1). All data will be collected from institution electronic medical records (EMRs), PRO portals, and other existing data sources, as needed.

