### **8.4 Patient Confidentiality**

No patient data will leave the health system IT systems as part of this project. Neither OM1 nor AHRQ will have access to any patient data as part of this project. All parties will ensure protection of patient personal data and will not include patient names on any study forms, reports, publications, or in any other disclosures, except where required by law.

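### Objective 1 claims technical feasibility of extraction and calculation, but the only planned assessment is a staff survey that measures neither

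*Protocol*

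**What the plan says.** Section 3 (Objectives) states the first aim as: "Demonstrate that it is technically and operationally feasible to use an open-source app to extract the selected outcome measures". PHQ-9 data are named among the inputs, and the sources are the clinical systems already in place. The objective also asks the app to "provide the calculated measure results in the" workflow of the treating clinician. Section 4.1 describes the chain this requires. The app connects to the site EHR and is then to "aggregate EHR and PRO data, calculate the outcome measure results, and return the results to the EHR". The same section says: "Baseline data on patient characteristics, treatments, and symptoms will be combined with longitudinal data on outcomes during the study timeframe".

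Section 5 (Qualitative Assessment) gives the aim of the analysis: "The purpose of this analysis is to assess the feasibility and value of the open-source app". It names one instrument. Clinicians and other personnel, with IT staff as the example, "will be asked to complete a brief web-based survey at the conclusion of the data collection period to provide feedback on the app". The survey has about 20 questions in three domains: usability, burden, and overall value for patient care and engagement. Section 5 plans no formal statistical analysis, reports no sample size calculation, expects about 50 patients at five practices to be enough for the objectives, and ends: "No patient data will be included in the assessment phase".

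Section 8.4 (Patient Confidentiality) adds: "Neither OM1 nor AHRQ will have access to any patient data as part of this project". Sections 4.6 and 6.1 keep all data inside the health system's IT systems.

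**The concern.** Whether the app found the inputs, returned a result and calculated it correctly can be observed for each patient, measure and timepoint. The assessment observes none of these. It collects staff views and sets no criterion against which feasibility could be judged.

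The measures leave room for faults that staff would not notice. Section 4.4 requires an initial PHQ-9 above 9, windows of 60 days either side of 6 and 12 months, a 50% reduction for response, and at least two months of remission before recurrence. Recurrence also combines PHQ-9 scores with hospitalization data. Section 1 itself names EHR extraction as the first barrier raised by stakeholders. It reports that they wanted pilots to show that data of sufficient quality for registry research can be generated.

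At stake is whether the final report can support its main claim. A positive survey would be compatible with low completeness or with a wrongly implemented measure, and no planned result could count against technical feasibility.

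**Working it through.** **The plan's own figure.** The only figure is about 50 patients at five practices (Sections 4.2 and 5). It cannot be reproduced, because the protocol gives no rate, precision target, error level or success threshold.

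**Objective against assessment.** The steps come from Sections 3 and 4.1, the instrument from Section 5.

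| Step in objective 1 | What the survey can give | Planned measurement |
|---|---|---|
| App installed and connected to the EHR | IT staff report | None beyond that report |
| Inputs extracted from EHR and PRO system | Impression only | None |
| Measure calculated correctly | Not covered by any of the three domains | None |
| Result returned to the workflow | Impression of availability | None |
| Workable in practice | Usability and burden items | Survey summary |

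The last row is served and the first partly. The three in between, which carry the technical claim, have no measured quantity.

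**Unit of analysis.** Section 5 says 50 patients suffice for the objectives, but under the same section they supply no data to the assessment. The units assessed are survey respondents, whose number is not stated. The sufficiency claim therefore attaches to no analysis.

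**What local counts could deliver.** Exact (Clopper-Pearson) 95% limits for x of n are the 2.5% quantile of Beta(x, n − x + 1) and the 97.5% quantile of Beta(x + 1, n − x). When x = n, the lower limit is 0.025^(1/n) = exp(−3.689/n).

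With all 50 patients evaluable:
- 50/50: exp(−3.689/50) = 0.929, so 92.9% to 100%
- 45/50: 78.2% to 96.7%
- 40/50: 66.3% to 90.0%

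Remission, response and recurrence apply only to patients with an initial PHQ-9 above 9, and recurrence also needs a prior remission of at least two months. The protocol does not say how many patients will qualify, so the eligible number n is an assumption. The lower limit when every eligible result is correct would be:
- n = 40: exp(−3.689/40) = 0.912
- n = 30: exp(−3.689/30) = 0.884
- n = 20: exp(−3.689/20) = 0.832

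At n = 30, a result of 27/30 gives about 74% to 98%. Missing follow-up scores would reduce n further.

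**Two limits on these intervals.** First, a criterion requiring the lower limit to exceed, say, 95% could not be met, since a perfect 50/50 reaches only 92.9%. Any criterion has to apply to the observed proportion. Second, the patients sit in five practices of one health system, on average 50/5 = 10 per practice. A field-mapping or calculation fault would tend to affect every patient on that measure, so the independence behind the binomial interval is doubtful.

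**The case against.** The strongest reply is that this is a pilot with no formal analysis, and that running the app at five practices and surveying those who ran it is itself evidence of feasibility. Much of this stands. Objective 1 covers operational as well as technical feasibility, usability and burden bear directly on the former, and IT staff can report whether the app worked. A reader might infer that the survey can show nothing about feasibility; the protocol does not support that. What is missing is measured completeness, return rate and accuracy.

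A reader might also infer that Section 5 forbids even aggregate counts. The text does not settle this. Its closing sentence follows the survey description and may mean only that no patient records enter the survey assessment. The supportable statement is that no technical measure is specified and that the wording leaves counts in doubt.

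A third tempting inference is that clinicians will be shown unverified results, which would be a patient-safety problem. The protocol neither describes nor excludes software verification before deployment, so this would be an argument from silence. Clinicians who saw blank results would also probably mark the app down.

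Deferring to an unseen statistical analysis plan does not help. Section 5 itself fixes the method, and an analysis of patient records added elsewhere would conflict with its last sentence on a plain reading. Nor does confidentiality stand in the way: Sections 4.6, 6.1 and 8.4 keep records inside the health system, and counts produced there are compatible with that.

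**Conclusion.** The mismatch is real and lies in the protocol's stated method. Objective 1 makes a technical claim, and the assessment in Section 5 produces no estimate of extraction completeness, result return or calculation accuracy. It does produce evidence on operational feasibility and on whether the app ran.

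The conclusion rests on reading Section 5 as the whole of the planned assessment, since no other is named. It does not rest on the precision obtainable from 50 patients. That precision is modest, with a lower limit of at most 92.9% and, under the assumed eligible numbers of 20 to 40, at most 83.2% to 91.2%. The value of the counts is descriptive: they would show gaps and mismatches that a survey may miss.

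For a pilot without hypothesis testing, this is a point that should be fixed rather than one that invalidates the study.

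**What to change.** Replace the last sentence of Section 5 with: *No patient-level data leave the health system; the health system will report aggregate counts.*

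For each Section 4.4 measure and timepoint, report as n/N among patients eligible for that measure:
- inputs found in the EHR or PRO system
- result returned by the app
- result matching a scripted recalculation from the source fields, with every mismatch explained

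State in advance a feasibility criterion applied to the observed proportion, with the value set by the sponsor. Exact confidence intervals may be shown but should be labelled descriptive. Report whether clinicians opened the results only if the app already logs it: the protocol mentions no such log, and Section 4.6 rules out collecting data solely for the study. Rewrite the sufficiency statement for 50 patients so that it refers to these counts.

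The alternative is to narrow objective 1 to what the survey can show, namely staff-reported operational feasibility and value.

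The first route costs some health-system analyst time for a script on about 50 records. It also needs a check that the consent described in Section 8.3, which covers presenting data to clinicians in the app, extends to the counts. An amendment under Sections 6.2 and 8.5 may follow. The sponsor also accepts a feasibility claim that could fail.

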## **6. Study Management**

This study will be performed by OM1 in close collaboration with the health system, with guidance, input, review, and approval of AHRQ. The health system team will lead the engagement and support activities for the participating practices, including development of site recruitment materials and training materials, with support from the OM1 team. To ensure the quality and integrity of research, this study will be conducted under the *Guidelines for Good Pharmacoepidemiology Practices* issued by the International Society for Pharmacoepidemiology (ISPE), the principles outlined in the Declaration of Helsinki, and any applicable national guidelines.

### **6.1 Data Management**

All data will remain within the health system IT systems.

### **6.2 Changes to the Protocol**

Changes to the protocol will be documented in written protocol amendments. Major (i.e., substantial, significant) amendments will usually require submission to the relevant institutional review board (IRB) for approval or favorable opinion. In such cases, the amendment will be implemented only after approval or favorable opinion has been obtained. Minor (nonsubstantial) protocol amendments, including administrative changes, will be filed by at each participating site and will be submitted to the relevant IRB.

### **6.3 Study Governance**

OM1 will be responsible for providing appropriate oversight of all scientific, technical, financial, and administrative matters related to this project, under the direction of [name] as the Project Director.

### **6.4 Publication Policy**

Any publication of the results from this study will be guided by the Uniform Requirements for Manuscripts Submitted to Biomedical Journals: Writing and Editing for Biomedical Publication of the International Committee of Medical Journal Editors (ICMJE), updated December 2018. The rights of the participating sites and of OM1 with regard to publication of the results of this study are described in the site contract.

## **7. Safety Reporting**

Due to the observational nature of the study and the use of existing data sources, no adverse event reporting is required. No specific medicinal products or devices are being evaluated as part of the study and there are no objectives related to safety.

## **8. Ethical and Regulatory Considerations**

### **8.1 Guiding Principles**

The study will be conducted in compliance with the US Food and Drug Administration (FDA) Title 21 Code of Federal Regulations (CFR) Part 50 – Protection of Human Patients and Part 56 – Institutional Review Boards; the International Council for Harmonisation for Pharmaceuticals for Human Use (ICH) Good Clinical Practice (GCP) guidelines E6R2 (November 09, 2016) as they apply to post-marketing, observational studies; the Guidelines for Good Pharmacoepidemiology Practices (GPPs) issued by the International Society for Pharmacoepidemiology (ISPE); the Belmont Report; US Title 45 CFR Part 164 Subpart E – Privacy of Individually Identifiable Health Information and the Health Insurance Portability and Accountability Act of 1996 (HIPAA) Privacy Rule (2002); and any applicable national guidelines.

### **8.2 Required Documents**

Prior to commencement of any study procedures, the protocol signature page, site contract, and IRB approval must be on file with OM1.

### **8.3 Patient Information and Informed Consent**

All data elements will be collected from information routinely recorded in the electronic medical record or as part of the patient's participation in one of the registries. No visits or examinations, laboratory tests, or procedures are mandated as part of this study. Patients will be asked to provide consent for their data to be presented to clinicians within the context of the open-source app.

### **8.4 Patient Confidentiality**

No patient data will leave the health system IT systems as part of this project. Neither OM1 nor AHRQ will have access to any patient data as part of this project. All parties will ensure protection of patient personal data and will not include patient names on any study forms, reports, publications, or in any other disclosures, except where required by law.

### **8.5 IRB**

Consistent with local regulations and prior to commencement of any study procedures, the study protocol will be submitted to the responsible IRB for its review. Enrollment will not start at any site before OM1 has obtained written confirmation of a favorable opinion/approval from the relevant central or local IRB. The IRB will be asked to provide documentation of the date of the

meeting at which the favorable opinion/approval was given that clearly identifies the study and the protocol version.

Before implementation of any substantial changes to the protocol, protocol amendments will also be submitted to the relevant IRB in a manner consistent with local regulations. It is the responsibility of the investigator to have prospective approval of the study protocol, protocol amendments, and other relevant documents, if applicable, from their local IRB and provide documentation of approval to OM1. All correspondence with the IRB should be retained in the Investigator File.

Should the study be terminated early for any unanticipated reason, the investigator will be responsible for informing the IRB of the early termination.

